- Diet instructions (for visit #1 and visit #1) Patients will be asked to maintain a moderate protein (1.5g/kg of weight), and high sodium diet (3,450 mg of sodium per day) for one week prior to the study visit #1, and between study visit #1 and #2.
- Copy of patient information and consent form to review

Study Visit #1

Visit #1 will take place at Adult CTRC or Barbara Davis Center. Medical history will be reviewed and eligibility determined. . Informed consent will be obtained from eligible participants following standard COMIRB approved methods by the PI and/or members of the research team.

At this visit, participants will present fasting from midnight, height, weight and blood pressure will be measured. Urine will be collected and blood will be obtained via venipuncture by RN or venipuncture-trained PRA. The baseline blood will be drawn for serum uric acid, serum glucose, serum creatinine and serum cystatin C. Urine will be collected for urine pH, urine ketones, urine glucose, urine creatinine and urine uric acid. The urine will also be examined for precipitation and crystallization of urine uric acid. The participant will take 1950mg of sodium bicarbonate (3 x 650mg tablets) with water. We estimate that the study visit will take 60 minutes. After completion of the study visit, the participant will receive the second dose of sodium bicarbonate to take approximately 12 hours after the first dose (1950mg of sodium bicarbonate [3 x 650mg tablets]).

The participants will need to remain on the moderate protein and high sodium diet until completion of study visit #2. We will have provide protein bars, or participants may bring their own high protein snack.

Study Visit #2:

Visit #2 will take place at Adult CTRC or Barbara Davis Center. Participants will present fasting from midnight. Urine will be collected and blood will be obtained via venipuncture by RN or venipuncture-trained PRA. Blood will be drawn for serum uric acid, serum glucose, serum creatinine and serum cystatin C. Urine will be collected for urine pH, urine ketones, urine glucose, urine creatinine and urine uric acid. The urine will also be examined for precipitation and crystallization of urine uric acid.

D. Description, Risks and Justification of Procedures and Data Collection Tools:

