In any clinical study unforeseen human factors provide challenges. The current study is based upon a previous study with sodium bicarbonate administration in adults with no reported adverse effects. Furthermore, we aim to use lower doses of sodium bicarbonate in this study. We have also performed careful power analyses to allow meaningful analyses.

F. Data Analysis Plan:

(A HIPAA compliant, Red Cap database system will be used for this study.)

| Outcome | Effect size | SD pre and post | Correlation of pre with post | SD of change | Power | Ν |
|--------------------|-------------|--------------------|------------------------------------|-----------------|-------|----|
| Urine pH | 0.5* | 0.42 | 0.5 | 0.42 | >99 | 20 |
| | 1.0* | 0.42 | 0.5 | 0.42 | >99 | 10 |
| Urine uric acid | 10% | 16.48 | 0.95 | 5.21 | 80 | 47 |
| | 20% | 16.48 | 0.80 | 10.42 | 80 | 47 |

Table 1 Power calculations:

* Units on the pH scale

Per our power analysis, with a sample size of 50 we will have power of 0.8 to detect effect size of 20% change in urine uric acid following 24-hours of NaHCO₃. Paired t-test will be employed to evaluate whether the change in urine uric acid pre- and post NaHCO3 administration is statistically significant. We will also adjust for covariates with ANCOVA or linear regression models [ANCOVA vs. linear regression models will be decided based on the variation of urine uric acid at baseline in our participants].

We will also calculate fractionated excretion of uric acid (FeUA = [(UUA * SCr / SUA * UCr)*100]), and regress FeUA, SUA and UUA on eGFR calculated by CKD-EPI creatinine and cystatin C. Furthermore, we will also regress blood glucose and urine glucose on FeUA, SUA and UUA.

G. Summarize Knowledge to be Gained:

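### The FeUA formula in Section IV.F lacks brackets around its denominator, so as printed it multiplies by urine creatinine; the supplementary FeUA regressions would be wrong if it were coded that way (minor).

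*Combined protocol and SAP*

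**What the plan says.** The formula appears once, in the last paragraph of Section IV.F. The sentence opens with "We will also calculate fractionated excretion of uric acid" and then gives "FeUA = [(UUA * SCr / SUA * UCr)*100", followed by a closing square bracket. The only inner brackets enclose the whole expression before the multiplication by 100. The formula is not restated or corrected elsewhere.

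Section IV.F then gives FeUA two uses. The plan will "regress FeUA, SUA and UUA on eGFR calculated by CKD-EPI creatinine and cystatin C", and "we will also regress blood glucose and urine glucose on FeUA, SUA and UUA". So FeUA is the outcome in the first set of models and a predictor in the second.

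All four inputs will be available. In Section IV.C, the text for each of the two study visits says "Urine will be collected for urine pH, urine ketones, urine glucose, urine creatinine and urine uric acid". For Visit #1 it says the baseline "blood will be drawn for serum uric acid, serum glucose, serum creatinine and serum cystatin C", and Visit #2 lists the same serum tests.

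**The concern.** A fractional excretion is a ratio of two clearances. Urine flow and urine concentration cancel, and the result is a pure number that can be given as a percentage. The printed expression does not have this property when read by the usual rule that multiplication and division run from left to right: urine creatinine moves from the denominator to the numerator.

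This is the plan's working definition of a derived variable, so a programmer could transcribe it directly. FeUA is also the only quantity in Section IV.F that uses urine creatinine, and hence the only stated analysis variable that corrects for how concentrated the urine is. The literal form reverses that correction. Section II itself expects concentration to vary, since it describes relative dehydration, with glucosuria among its causes, leading to concentrated urine. If the literal form were used, an association between FeUA and urine glucose could reflect urine concentration alone. At stake is the validity of the FeUA regressions.

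**Working it through.** The plan states no FeUA value, so there is no figure to reproduce. The check compares two readings of one expression.

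**Inputs.** UUA and SUA are urine and serum uric acid; UCr and SCr are urine and serum creatinine. The formula comes from Section IV.F. The documents give no concentrations, so the numbers below are assumed for illustration, in mg/dL: UUA 40, SCr 0.8, SUA 4.5, UCr 100.

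**Step 1: what the name requires.** With urine flow V, uric acid clearance is UUA × V / SUA and creatinine clearance is UCr × V / SCr. Their ratio is (UUA × SCr) / (SUA × UCr). V cancels and so do the units.

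**Step 2: what is printed.** Read left to right, the expression is ((UUA × SCr) / SUA) × UCr × 100, that is, 100 × UUA × SCr × UCr / SUA.

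**Step 3: ratio of the two.** Printed / bracketed = UCr × UCr = UCr². This holds for any inputs and needs no assumed value. At UCr of 50, 100 and 200 mg/dL the factor is 2,500, 10,000 and 40,000.

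**Step 4: numbers.**

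- Bracketed: 100 × (40 × 0.8) / (4.5 × 100) = 100 × 32 / 450 = 7.11%.
- Printed: 100 × 40 × 0.8 × 100 / 4.5 = 71,111.

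**Step 5: dilution and direction** (SCr 0.8 and SUA 4.5 throughout).

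| Case | UUA | UCr | Bracketed (%) | Printed |
|---|---|---|---|---|
| Reference | 40 | 100 | 7.11 | 71,111 |
| Urine half as concentrated | 20 | 50 | 7.11 | 17,778 |
| Urine twice as concentrated | 80 | 200 | 7.11 | 284,444 |
| UCr halved, UUA fixed | 40 | 50 | 14.22 | 35,556 |
| UCr doubled, UUA fixed | 40 | 200 | 3.56 | 142,222 |

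When UUA and UCr change together, as in simple dilution, the bracketed form is constant and the printed form moves with the square of concentration. If both concentrations fell by 20% between visits, the printed value would be multiplied by 0.8² = 0.64, a fall of 36%, while the true fractional excretion stayed the same. When UCr alone rises, the bracketed value falls and the printed value rises.

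**Step 6: units.** Multiplying both creatinine values by a conversion factor k leaves the bracketed form unchanged and multiplies the printed form by k². The conversion of uric acid units cancels in both. With k = 88.4 (mg/dL to µmol/L, a factor not given in the documents), 71,111 becomes 71,111 × 7,814.56, or about 5.6 × 10⁸, and the bracketed form remains 7.11%. The printed quantity has units of concentration squared and cannot be a percentage.

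**The case against.** The strongest reply is that this is notation and not a wrong analysis. The sentence names the quantity, lists the four correct inputs in the customary order and scales by 100. Most readers would supply the missing brackets, and nothing suggests that anyone meant to multiply by urine creatinine. A literal result of the order of 71,111 percent would very probably be caught. All of this stands, and it keeps the severity low. It does not make the printed rule correct: an analysis plan should not depend on the programmer to repair the definition of a variable.

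A reader might infer that the fault runs through all of Aim 3, or that it threatens the study's main result. The documents do not support either reading. Section I states Aim 3 in terms of urine uric acid concentration, precipitation and crystallization, set against tubular-injury markers and eGFR. FeUA is not named in any aim or hypothesis, nor among the outcome measures in Section IV.A. In Section IV.F it is one of three variables in each regression statement; SUA and UUA are used there as measured. The glucose regressions belong to no stated aim. The paired t-test on urine uric acid, its covariate-adjusted models and Table 1 make no use of FeUA.

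One might also ask whether the formula was set as a stacked fraction in the source document, in which case the point would fall away. The inline asterisks and slash, with the other brackets intact, suggest that it was typed on one line.

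**Conclusion.** Wrong as written; minor. Under standard operator order, the printed formula is UCr² times the fractional excretion it claims to define. That result is exact and rests on no assumed concentrations; only the worked values such as 7.11% and 71,111 do. Because UCr differs between people and visits, the error is not a constant factor that a regression coefficient would absorb.

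The harm is conditional on the formula being coded literally, which is possible but not the likeliest outcome. It would then be confined to the supplementary models in which FeUA is the outcome against eGFR or a predictor of blood or urine glucose. Those models would be invalid, because the variable would be strongly driven by urine concentration.

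**What to change.** In Section IV.F, replace the expression with:

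FeUA (%) = 100 × (UUA × SCr) / (SUA × UCr)

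Add one clause: UUA and SUA are in the same units, UCr and SCr are in the same units, and all four values come from the same visit. The uric acid pair and the creatinine pair need not share a unit with each other. The same-visit wording is a clarification; it does not correct an error, since both visits already collect all four inputs.

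The cost is one line of text. Data collection, sample size and the other analyses do not change. If FeUA has already been programmed, check the code against the bracketed form.

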Labs methods: Serum creatinine, serum cystatin C, serum uric acid and serum glucose will be determined using standard methods in the CTRC core lab and [name]'s lab. Urine uric acid, urine glucose, urine creatinine and urine pH will be measured at [name]'s lab. Urine ketones will be checked at BDC.

Sample banking: Residual blood and urine volume will be stored for future research, in particular to use when new and promising urinary and serum biomarkers become available.

Sodium bicarbonate: Three tablets of 650mg of sodium bicarbonate (1950mg) will be given twice a day to all participants. [name] Pharm.D. will arrange and dispense medications. Prescriptions will be written for the dose to be taken by the participants at home.

Other forms: Standard medical history will be obtained (see accompanying forms in submission packet).

Estimation of GFR: Various equations have been developed to estimate GFR based on either serum creatinine or cystatin C plus other variables. We will employ the state of the art CKD-EPI combined creatinine and cystatin C to calculate estimated GFR in our participants.

CKD-EPI combined creatinine and cystatin C eGFR = eGFR = 135 x min(serum creatinine/k, 1)^{-a} x max(serum creatinine/k, 1)^{-0.601} x min(serum cystatin C/0.8, 1)^{-0.375} x max(serum cystatin C/0.8, 1)^{-0.711} x 0.995^{age} [x 0.969 if female] [x 1.08 if black]

Compliance:

To improve compliance, the first dose of sodium bicarbonate (1950 mg) will be administered at the visit #2 at CTRC. Moreover, participants will be asked to set an alarm on their phone for the second and final dose (1950mg) at home.

Plan to minimize risk:

1. Fasting and hypoglycemia:

Fasting will be limited to 8 hours, and detailed fasting and insulin instructions will be given to participants.

2. Venipuncture to draw blood for lab tests:

Venipuncture will be performed by research personnel with experience with venipuncture to reduce risk of pain. Gloves will be worn and the area of skin cleaned to prevent risk of infection.

3. Sodium bicarbonate administration:

The study participant will be monitored for a minimum of an hour after the administration of the first sodium bicarbonate dose to check for any reaction. The study participant will be told to call with any issues or concerns at home. Participants taking medications known to interact with sodium bicarbonate will be excluded from participating.

E. Potential Scientific Problems:

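### Minor: FeUA and the combined eGFR share one serum creatinine value, which builds a small negative slope into their regression; a cystatin-C-only eGFR avoids it at little cost

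*Combined protocol and SAP*

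**What the plan says.** Section IV.F defines fractional excretion as "FeUA = [(UUA * SCr / SUA * UCr)*100" and plans to "regress FeUA, SUA and UUA on eGFR calculated by CKD-EPI creatinine and cystatin C". The brackets around the denominator are missing, but serum creatinine (SCr) is in the numerator on either reading.

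Section IV.D, Estimation of GFR, commits to one equation: "We will employ the state of the art CKD-EPI combined creatinine and cystatin C to calculate estimated GFR in our participants". In it, creatinine above k enters as "max(serum creatinine/k, 1)^{-0.601" and below k with exponent −a. Neither k nor a is given a number. Cystatin C enters with exponent −0.375 below 0.8 and −0.711 above.

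Under Study Visit #1 in IV.C, "The baseline blood will be drawn for serum uric acid, serum glucose, serum creatinine and serum cystatin C", and the same four tests are listed for Study Visit #2. Section IV.D also acknowledges that creatinine-free equations exist: "Various equations have been developed to estimate GFR based on either serum creatinine or cystatin C plus other variables". The plan does not mention the shared creatinine, offers no sensitivity analysis for it, and does not say which visit supplies the data for this regression.

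**The concern.** When outcome and predictor are computed from the same measured quantity, with opposite signs, error in that quantity produces an association by itself. Here a creatinine result that is too high by chance raises FeUA and lowers eGFR for that participant, and one that is too low does the reverse. A negative FeUA–eGFR slope would probably be read as a link between uric acid handling and glomerular function, the general subject of Specific Aim 3. Part of it would be arithmetic, and the plan has no means of showing how much.

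**Working it through.** The plan states no figure for this regression, so there is none to reproduce.

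**Direction, from the printed formulas.**

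ln FeUA = constant + ln UUA + ln SCr − ln SUA − ln UCr

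ln eGFR = constant − b·ln SCr − c·ln(cystatin C) + age, sex and race terms

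b is 0.601 above k and a below it; c is 0.711 or 0.375. SCr has power +1 in one and −b in the other, so an error in SCr with log-SD s_e contributes covariance −b·s_e², which is always negative.

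**A coherent null.** Let SCr = creatinine generation ÷ GFR × error, and let true FeUA be unrelated to GFR. Generation cancels between SCr and UCr, so only the SCr error is shared:

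r = −b·s_e² ÷ [√(s_F² + s_e²) × s_E]

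Here s_F is the log-SD of true FeUA and s_E the log-SD of eGFR, with

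s_E² = (b + c)²·s_GFR² + b²·s_gen² + b²·s_e² + c²·s_cys²

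**Assumed inputs (none is in the documents).** s_e 0.05–0.12; s_F 0.3–0.5; s_GFR 0.15; s_gen (creatinine generation) 0.20; s_cys (cystatin C error) 0.08; a = 0.2 where the lower creatinine branch applies; two-sided 0.05. From the documents: n = 47 (IV.B; the text under Table 1 says 50) and the printed exponents. At n = 47, significance needs |r| of at least 0.288.

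**Mild setting** (s_e 0.05, s_F 0.5, b 0.2, c 0.375):
- s_E² = (0.575 × 0.15)² + (0.2 × 0.20)² + (0.2 × 0.05)² + (0.375 × 0.08)² = 0.0074 + 0.0016 + 0.0001 + 0.0009 = 0.0100, so s_E = 0.100.
- √(0.25 + 0.0025) = 0.5025.
- r = −0.0005 ÷ (0.5025 × 0.100) = −0.010. False-positive rate: about 5%.

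**Severe setting** (s_e 0.12, s_F 0.3, b 0.601, c 0.711):
- s_E² = (1.312 × 0.15)² + (0.601 × 0.20)² + (0.601 × 0.12)² + (0.711 × 0.08)² = 0.0387 + 0.0144 + 0.0052 + 0.0032 = 0.0616, so s_E = 0.248.
- √(0.09 + 0.0144) = 0.323.
- r = −0.00865 ÷ (0.323 × 0.248) = −0.108. By Fisher's z with standard error 1/√44, the false-positive rate is about 11%.

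**Simulation.** Runs at n = 47 (at least 8,000 replicates per setting), with creatinine error of 5%, 8% and 12% and b from 0.2 to 0.6, gave mean r from −0.007 to −0.125 and false-positive rates from 4.9% to 13.1%. The largest result corresponds to an eGFR log-SD of about 0.214: 0.00864 ÷ (0.323 × 0.214) = 0.125. With error of 8% or less, r stayed between −0.007 and −0.061 and the false-positive rate did not exceed 6.4%.

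**After the fix.** With a cystatin-C-only eGFR in the same simulations, mean r was −0.002 to +0.002 and the false-positive rate 4.7% to 5.1%, which is nominal.

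**The case against.** The strongest reply is that the effect is small and the model peripheral. Both parts stand. A built-in r of −0.01 to −0.13 cannot account for an observed r of −0.4, or for any positive slope. Hypothesis 3.2 names urine uric acid concentration, precipitation and crystallization, not FeUA. SUA and UUA contain no creatinine, and the study describes itself as a pilot. What survives is that the bias has a known sign, the plan does not acknowledge it, and the remedy uses data already collected.

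Some stronger readings are tempting but unsupported:

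- A reader might infer that a real association could never be distinguished from shared creatinine. That conclusion comes from letting SCr vary with log-SD 0.20 independently of everything else. With log-SDs of 0.40 for UUA/UCr, 0.25 for SUA and 0.15 for cystatin C, SD(ln FeUA) = √(0.16 + 0.0625 + 0.04) = 0.512, SD(ln eGFR) = √[(0.601 × 0.20)² + (0.711 × 0.15)²] = 0.161, and r = −(0.601 × 0.04) ÷ (0.512 × 0.161) = −0.29. This is not a coherent null. If GFR drives creatinine, cystatin C moves with it; if creatinine production drives it, UCr moves too and the effect cancels in FeUA. What remains is a 20% pure creatinine error, for which the documents give no basis. If the variation is instead true GFR variation with UUA/UCr and SUA unrelated to it, FeUA really does fall as GFR rises. A cystatin-C-only eGFR would show that as well.
- A reader might extend the point to the plan to "we will also regress blood glucose and urine glucose on FeUA, SUA and UUA". Neither glucose measure contains creatinine, so this argument does not reach those models.
- A reader might infer that both visits will be pooled as independent rows. The plan does not say so.

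**Conclusion.** The point holds as a minor one about a secondary analysis. The shared term and its negative sign follow from the printed formulas and need no assumption. The size does: with 5–12% short-term creatinine error, the built-in r is about −0.01 to −0.13 and the false-positive rate about 5–13% at n = 47. The bias may therefore be negligible. These figures rest on assumed spreads and on how many participants lie above k, which the documents do not give. A narrower eGFR spread, which the exclusion of prior low eGFR or albuminuria might produce, would raise them somewhat. Materially larger values need creatinine to vary independently of cystatin C and urine creatinine. The paired t-test on urine uric acid, the SUA and UUA regressions and Hypothesis 3.2 are not affected.

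**What to change.** In IV.F, make a cystatin-C-only eGFR the regressor for the FeUA model, and name and print the equation, because IV.D gives only the combined one. At minimum, report that model beside the combined-eGFR model and state that the latter shares serum creatinine with its outcome. Keep the combined eGFR for SUA and UUA.

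Specify that the FeUA model uses the pre-dose sample, rather than a visit number. IV.B describes visit #1 as a consent visit and refers to fasting for visits #2 and #3. IV.C takes samples at visits #1 and #2 and gives the first dose at visit #1. The Compliance paragraph in IV.D puts the first dose at visit #2. These passages should be reconciled.

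The cost is a few lines of text and one more computed variable, with no new sample or visit. There are two limits. A cystatin-C-only eGFR may be somewhat less precise than the combined one. FeUA also stays scaled to creatinine clearance by definition, so the change removes the shared measurement but not that property. If the cystatin-C-only equation replaces the combined one for FeUA alone, the three parallel models will not share a regressor; reporting both for FeUA deals with that.

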Serum uric acid (SUA) is lower in adolescents and adults with type 1 diabetes compared to non-diabetic peers (4, 5). Despite lower levels SUA remains an important risk factor for diabetic nephropathy in type 1 diabetes (6), with a large clinical trial underway examining the ability of allopurinol to prevent early renal loss (7). Several mechanisms have been proposed to explain the lower levels of SUA in type 1 diabetes including glucosuria induced uricosuria leading to spilling of urine uric acid (UUA) and lowering of SUA (8), and the notion that intracellular uric acid (IUA) and/ or UUA rather than SUA may be responsible for the development of complications. Animal studies have demonstrated that blocking uric acid production protects the kidney from tubulointerstitial injury, which suggests a causal role for uric acid in the development of diabetic tubular injury (9, 10). Relative dehydration, secondary to glucosuria, exercise or inadequate liquid intake, may lead to concentrated and acidic urine, which may cause UUA to precipitate and crystallize in type 1 diabetes (11-14). The UUA precipitation and crystallization is thought to induce inflammation and injury of the tubules with possible retrograde glomerular injury (11-14). Moreover, it was recently shown that UUA promoted apoptosis in human proximal tubular cells by oxidative stress and activation of NADPH Oxidase NOX 4 (15).

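### The urine glucose–UUA regression pairs two uncorrected concentrations from one urine sample, so its slope cannot be read as evidence on uric acid excretion; the planned FeUA regression should carry that question

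*Combined protocol and SAP*

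**What the plan says.** After the paired test of urine uric acid, Section IV.F (Data Analysis Plan) adds regressions on eGFR and then states that "we will also regress blood glucose and urine glucose on FeUA, SUA and UUA". No transformation, visit, significance level, power or rule of interpretation is given for these regressions. The preceding paragraph promises covariate adjustment, but it names no covariate and refers to the pre/post uric acid comparison.

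The urine variables come from one collection per visit. Under Study Visit #1 in Section IV.C the plan says: "Urine will be collected for urine pH, urine ketones, urine glucose, urine creatinine and urine uric acid". Visit #2 repeats the list. No timed collection or volume is described. That these are spot samples is an inference; the documents do not use the term.

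In the analysis plan, urine creatinine is used only to form FeUA: "We will also calculate fractionated excretion of uric acid (FeUA = [(UUA * SCr / SUA * UCr)*100".

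Section II (Background and Significance) lists, among the proposed reasons for low serum uric acid in type 1 diabetes, "glucosuria induced uricosuria leading to spilling of urine uric acid (UUA) and lowering of SUA". It also says that urine concentration varies in this population and names glucosuria as one cause.

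**The concern.** A urine concentration is the amount excreted divided by the volume of water it is excreted in. UUA and urine glucose from one sample share that divisor. Suppose the two excretions are unrelated. A participant with concentrated urine still has both values high, and one with dilute urine has both low. A zero slope between the concentrations is then not what unrelated excretion predicts, and the usual regression test has the wrong size for the excretion question.

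If glucose draws water into the urine, the distortion can go the other way, because high glucose then lowers UUA. Neither a positive, a negative nor a flat slope speaks clearly to excretion.

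At stake is a secondary inference. A positive slope could be reported as support for the mechanism in Section II when it shows only that some participants gave more concentrated urine. The pre/post test is a separate matter, and changing it would not alter this cross-sectional association.

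**Working it through.** **1. Inputs from the documents.** Table 1 gives two urine uric acid rows: "10% | 16.48 | 0.95 | 5.21 | 80 | 47" and "20% | 16.48 | 0.80 | 10.42 | 80 | 47". The text gives N = 50 ("with a sample size of 50 we will have power of 0.8"). No significance level is stated, so two-sided 5% is assumed.

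**2. Reproducing Table 1.** SD of change = SD × √(2(1 − r)).
- 10% row: 16.48 × √0.10 = 5.21, as stated.
- 20% row: 16.48 × √0.40 = 10.42, as stated.

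N = 47 cannot be reproduced outright because the baseline UUA mean is not given. It can be back-solved. A paired t-test with N = 47 and 80% power detects a standardised effect of 0.417.
- 20% row: 0.417 × 10.42 = 4.35, and 4.35 / 0.20 gives a mean of about 21.7.
- 10% row: 0.417 × 5.21 = 2.17, and 2.17 / 0.10 gives about 21.7.

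The rows agree. The implied CV is 16.48 / 21.7 = 0.76. The normal approximation gives a mean of 21.29 and a CV of 0.77. For a lognormal, log-SD = √ln(1 + CV²), about 0.67 to 0.68.

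**3. Model with no true link.** UUA = U × D and urine glucose = G × D. Here U is uric acid excretion, G glucose excretion and D a shared concentration factor, all independent lognormals. The induced log-scale correlation is

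ρ = σ_D² / √[(σ_D² + σ_U²)(σ_D² + σ_G²)].

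Example: dilution is half of the log-variance of UUA (σ_D² = σ_U² = 0.5 × 0.684² = 0.234) and σ_G = 1.0. Then ρ = 0.234 / √(0.468 × 1.234) = 0.31. The critical correlation is 0.288 at N = 47 and 0.279 at N = 50, so the choice between 47 and 50 hardly matters here.

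**4. Simulated rejection, raw scale, N = 47, 20,000 runs per cell.** The documents give neither the dilution share nor the spread of urine glucose excretion. Both are assumed over a range.

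| Dilution share of UUA log-variance | σ_G 0.5 | σ_G 1.0 | σ_G 1.5 | σ_G 2.0 |
|---|---|---|---|---|
| 0% | 5.0% | 4.8% | 5.0% | 5.2% |
| 25% | 38.6% | 16.0% | 10.2% | 8.9% |
| 50% | 83.6% | 37.6% | 20.0% | 13.6% |
| 75% | 99.2% | 64.3% | 33.3% | 20.8% |

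Wherever dilution varies, nearly all rejections are positive. A narrower set of assumptions (dilution log-SD 0.3 to 0.5, σ_G 0.5 to 1.5) gives about 8% to 90%, and 23% at dilution log-SD 0.4 with σ_G 1.0.

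**5. If glucose dilutes the urine.** Let log D fall by k per log unit of glucose excretion. The log-scale covariance becomes σ_D² − k(1 − k)σ_G², with σ_D² now the part of dilution unrelated to glucose. With σ_D² = 0.234:
- k = 0.3, σ_G = 1.0: 0.234 − 0.21 = +0.024, close to zero.
- k = 0.2, σ_G = 1.5: 0.234 − 0.36 = −0.126, reversed.

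Simulated raw-scale rejection for k = 0.1 to 0.3 and σ_G = 1.0 to 1.5 is 3.6% to 20.9%. At k = 0.3 and σ_G = 1.5 it is 9.6%, of which 9.2 points are negative slopes. Strong positive inflation survives where glucose varies little: 42% to 81% at σ_G 0.5, k = 0.3 and dilution log-SD 0.4 to 0.5.

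**6. Alternatives under the model of step 3** (creatinine excretion log-SD 0.25, assumed; cells with dilution present).
- FeUA with UCr in the denominator, against urine glucose: 4.6% to 5.2%. D cancels in UUA/UCr, so this also holds when glucose dilutes the urine.
- Both analytes divided by UCr: 6.8% to 38% raw and 6.4% to 44% log, because the denominator is shared.
- Log model with log UCr as covariate: 5.6% to 36%, and 9.2% at a 50% share with σ_G 1.0.

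**7. The FeUA formula as typed.** Read left to right, UUA × SCr / SUA × UCr puts UCr in the numerator. D would then enter twice instead of cancelling, and the result for FeUA in step 6 would not apply.

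**The case against.** A reader might infer that shared dilution by itself makes this regression reject, and that the trial will therefore falsely support glucosuria-driven uricosuria. The documents do not support that. Both governing variances are absent from them, and rejection is near certain only if dilution dominates and urine glucose varies little. Section II itself ties urine concentration to glucosuria, so dilution independent of glucose is not the obvious model; once the two are linked, the bias can vanish or reverse.

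It is also fair to say that no aim or hypothesis concerns glucose, and that Section IV.F does not promise to read the UUA slope as evidence on excretion. The declared outcome includes urine uric acid concentration, and for precipitation the water content is part of the pathway. The same sentence already includes FeUA. The wording could also mean one joint model with FeUA, SUA and UUA together, which was not simulated.

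These points limit the size and the severity. What stands is that the plan lists UUA and FeUA side by side with no word on which answers the excretion question, and only FeUA removes the shared water.

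**Conclusion.** The concern holds in a limited form. The urine glucose–UUA slope confounds excretion with water content and cannot serve as evidence on glucosuria-driven uricosuria, whatever its sign. With independent dilution, false rejection runs from about 8% to 90% over the narrower assumed range and up to 99% over the wider one. With glucose-driven dilution it can be near 5%, or the slope can be negative. FeUA, correctly bracketed, keeps its nominal size.

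This rests on lognormal variables, separate simple regressions, two-sided 5%, N = 47, a UUA spread back-solved from Table 1, and assumed dilution, glucose and creatinine variances. The FeUA result also takes creatinine excretion and the serum values to be unrelated to glucose. That a misleading slope will be obtained, or will be interpreted as uricosuria, is a possibility and not something the plan commits to. Severity is minor: the paired comparison and the sample size are unaffected.

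**What to change.** In Section IV.F:
- Name the already planned urine glucose–FeUA regression as the analysis of uric acid excretion.
- Write the formula as FeUA = (UUA × SCr) / (SUA × UCr) × 100.
- Label the urine glucose–UUA regression descriptive. If it is kept, fit it on the log scale with log urine creatinine as a covariate, and say that this reduces the bias without removing it.
- Do not divide both analytes by urine creatinine.

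The cost is a sentence or two. Every variable is already measured at both visits. One secondary regression is downgraded. Urine glucose in the FeUA model remains a concentration, so the test has the right size but its slope does not measure glucose excretion; the plan should say so.
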